### 13.3 Sample size, accrual time and study duration

#### 13.3.1 Sample size

The study design to be utilized is fully described in [Section 13.1](#). There will be 16 evaluable patients assigned to each cohort (total of 32 evaluable patients). We anticipate accruing an additional 2 patients in each cohort to account for ineligible patients or cancellations. Thus the maximum target accrual is 36 in total. In the event that the additional accrual does not produce the required number of evaluable patients, we retain the option of continuing accrual until that goal is met.

#### 13.3.2 Accrual rate and duration

This phase II study is designed to accrue 16 evaluable patients in each cohort, over approximately 2-4 years. There is little information available for what the precise accrual rate will be. However our goal is to accrue the 32 evaluable patients (with an anticipated maximum of 36 patients to get 32 evaluable) within 2-4 years.

#### 13.3.3 Primary endpoint completion date for clinicaltrials.gov reporting

For purpose of ClinicalTrial.gov reporting, the Primary Endpoint Completion Date (PECD) for this study is the time the last patient registered has been followed for at least six months after being taken off the study treatment.

### 13.4 Supplementary analysis plans

#### 13.4.1 Secondary Endpoints

- **Progression free survival:** progression free survival (PFS) will be estimated using the C Kaplan-Meier method within each cohort. Median PFSs and survival rates will be estimated with their 95% confidence intervals. No formal comparison will be made among the cohorts.
- **Toxicity:** As per NCI CTCAE v 4.0, the term toxicity is defined as adverse events that are classified as possibly, probably, or definitely related to study treatment. Toxicities will be evaluated via the ordinal CTCAE standard toxicity grading. Overall toxicity incidence as well as toxicity profiles by patient and treatment cohort will be explored and summarized. Frequency distributions, graphical techniques and other descriptive measures will form the basis of the analysis. No formal comparison will be made among the cohorts.
- **Response as defined by Enhancing Volume:** Response by Enhancing Volume will be estimated using Response Rate (RR) - where response rate is defined as the number of responses achieved during treatment with BRAF and MEK inhibitors divided by the total number of evaluable patients. For this endpoint, only decreasing volume in enhancing disease will count toward the criteria for response. The same thresholds for CR and PR as seen in Section 11.0 will be used. Point estimates will be generated for response rates within each cohort with corresponding 95% binomial confidence intervals (Duffy and Santner).
- **Response as defined by Non-Enhancing Volume:** Response by Non-Enhancing Volume will be estimated using Response Rate (RR) - where response rate is defined as the number of responses achieved during treatment with BRAF and MEK inhibitors divided by the total number of evaluable patients. For this endpoint, only decreasing volume in non-enhancing disease will count toward the criteria for response. The same thresholds for CR and PR as seen in [Section 11.0](#) will be used.

Point estimates will be generated for response rates within each cohort with corresponding 95% binomial confidence intervals (Duffy and Santner).

- **Overall Survival:** overall survival (OS) will be estimated using the Kaplan-Meier method within each cohort. Median overall survivals and survival rates will be estimated with their 95% confidence intervals. No formal comparison will be made among the cohorts.
- **Duration of Response:** Duration of response is defined from the time measurement criteria are met for CR or PR (whichever is first recorded) until the first date that progressive disease or death is documented. Only patients who have achieved a CR or PR will be included in this analysis. Patients who fail to return for evaluation or patients who are still alive and have not progressed at the time of analysis will be censored for progression at the time of the last tumor assessment. Duration of response will be estimated using the Kaplan-Meier method within each cohort. Median overall survivals and survival rates will be estimated with their 95% confidence intervals. No formal comparison will be made among the cohorts.

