## 1.0 BACKGROUND

### 1.1 The natural history of craniopharyngioma

Craniopharyngiomas, which occur at an average age-adjusted incidence rate of 0.18 per 100,000, are epithelial tumors that arise in the pituitary stalk along the path of the craniopharyngeal duct. There are two main subtypes of craniopharyngiomas, the adamantinomatous form that is more common in children and the papillary form that predominantly occurs in adults. Located in or above the sella turcica, these tumors grow adjacent to the optic chiasm and often extend to involve the hypothalamus, cranial nerves, the ventricular system, visual pathways and major blood vessels at the base of the brain. Craniopharyngiomas can cause profound clinical sequelae both in the pediatric and adult populations, both through mass effect at presentation and through morbidity of treatment. At initial presentation, a broad range of signs and symptoms can be observed. Visual deficits, neuroendocrine deficiencies and severe headaches are common. Attempted surgical resection is usually the initial treatment of craniopharyngioma, but because these tumors adhere to critical brain and vascular structures, incomplete resection is common. Incompletely excised tumors have a propensity to recur, frequently with cysts, with firm adhesions between the recurrent tumor and the surrounding structures such that curative surgery is exceedingly difficult. Either the cystic, solid or both components, of craniopharyngiomas can cause significant symptomatic mass effect. As a result, most patients suffer lifelong sequelae that include panhypopituitarism, visual defects, impaired intellectual function and wide-ranging hypothalamic dysfunction leading to sleep disorders, abnormal thermo-regulation, and diabetes insipidus as well as hyperphagia and uncontrollable obesity. Radiation therapy, often used as an adjunct after surgery, can contribute to these complications. The debilitating long-term morbidities can have significant psychosocial impact on patients. No effective treatment besides surgery and radiation is known for craniopharyngiomas, and incomplete knowledge of the molecular mechanisms that drive craniopharyngiomas has hampered the development of targeted therapies for this tumor.

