### **2.2 Secondary objectives**

- 2.2.1** To determine the progression-free survival of patients with papillary craniopharyngiomas receiving BRAF and MEK inhibitors.
- 2.2.2** To determine the toxicity of BRAF/MEK inhibitors in patients with papillary craniopharyngiomas.
- 2.2.3** To determine the activity of BRAF and MEK inhibitor combination in papillary craniopharyngiomas as measured by response of enhancing volume of craniopharyngioma.
- 2.2.4** To determine the activity of BRAF and MEK inhibitor combination in papillary craniopharyngiomas as measured by response of nonenhancing volume of craniopharyngioma.
- 2.2.5** To determine the overall survival of patients with papillary craniopharyngiomas receiving BRAF and MEK inhibitors.
- 2.2.6** To determine the duration of response in patients with papillary craniopharyngiomas receiving BRAF and MEK inhibitors

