### 3.3.2 Measurable disease as defined in [Section 11.0](#).

- Measurable disease, defined as bidimensionally measurable lesions with clearly defined margins by MRI scans, with a minimum diameter of 10mm in both dimensions.
- Progressive disease required in cohort B, defined as any progressive measurable disease after surgery and radiation. Progressive or recurrent disease is not required in cohort A, but is allowed provided it is a new diagnosis and patient has not received prior treatment.

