**11.2 Definitions of measurable and non-measurable disease****11.2.1 Measurable disease**

Bidimensionally measurable lesions with clearly defined margins by MRI scans, with a minimum diameter of 10mm in both dimensions. Necrosis or cystic changes (nonenhancing disease) should be measured separately from and summed with contrast enhancing disease for measurements of tumor area.

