#### 13.2.2 Statistical design

Simon's two-stage design with one interim analysis for futility will be applied to evaluate RR within each cohort. The decision rules are included in [Section 13.2.3](#). Each cohort will require 16 evaluable patients. For the entire study, a total of 32 evaluable patients are required. Within each cohort, a total of 16 evaluable patients provides 89% power to detect a true response rate of at least 30%, with a one-sided significance level of 0.041 against the null hypothesis of 5% response rate. The overall family-wised type I error rate is 0.08. The following table shows the study characteristics of the design within each cohort:

If the true success proportion is ...	0.05	0.10	0.15	0.20	0.25	0.30
then the probability of declaring that the regimen warrants further studies is ...	0.041	0.201	0.422	0.628	0.785	0.886
and the probability of stopping at stage 1 is ...	0.630	0.387	0.232	0.134	0.075	0.040

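### The non-enhancing volume response rate in Section 13.4.1 is divided by all evaluable patients, although nothing requires a non-enhancing component at baseline

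*Combined protocol and SAP*

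**What the plan says.** Objective 2.2.4 is to determine activity "as measured by response of nonenhancing volume of craniopharyngioma"; objective 2.2.3 is its counterpart for enhancing volume. Section 13.4.1 turns each into a response rate: the number of responses during treatment "divided by the total number of evaluable patients". For the one rate, "only decreasing volume in non-enhancing disease will count toward the criteria for response"; for the other, "only decreasing volume in enhancing disease will count toward the criteria for response". Both reuse the CR and PR thresholds of Section 11.0, which for volumetric central review (11.4.5.4) means a fall of at least 20% from baseline for PR. Each rate is to be estimated by cohort with a 95% binomial interval. On cohort size, Section 13.2.2 says: "Each cohort will require 16 evaluable patients".

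Section 3.3.2 sets eligibility on "bidimensionally measurable lesions with clearly defined margins by MRI scans, with a minimum diameter of 10mm in both dimensions". Section 11.2.1 uses the same size rule and adds: "Necrosis or cystic changes (nonenhancing disease) should be measured separately from and summed with contrast enhancing disease". The key eligibility summary gives a minimum of 1 cm³ on imaging, also without naming a component.

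**The concern.** The objective asks what the drugs do to the non-enhancing part of the tumor. Only patients who have such a part can answer that question. Measurability rests on the whole lesion with its components summed, so a patient with a wholly enhancing tumor can enroll, be evaluable, and enter the denominator of the non-enhancing rate with no possibility of entering the numerator.

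This differs from the usual conservative practice of counting an unassessed patient as a failure. That patient could have responded; a patient without the component could not. The reported rate then mixes drug activity with the composition of the enrolled tumors, and a low value could reflect either. With 16 patients per cohort, a few such patients move the estimate noticeably.

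**Working it through.** **1. Can a patient without the component be enrolled and counted?**

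- Sections 3.3.2 and 11.2.1 apply the 10 mm rule to the lesion, and 11.2.1 sums the components. Nothing in the documents requires a non-enhancing part.
- Section 13.4.1 does not limit the denominator to patients who have the component, and does not say how to classify a baseline of zero.
- The word evaluable is not defined. Section 13.2.1 uses the same denominator for the primary endpoint, and 13.3.1 ties the extra accrual to ineligibility and cancellation. Neither refers to tumor composition.

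**2. How is that patient scored?** PR needs a fall of at least 20% from baseline, which is undefined at a baseline of zero. Since only a decrease counts, the patient is a non-responder.

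**3. Effect on the rate.** Let *N* be the evaluable patients in a cohort (16, from 13.2.2), *a* the number without the component, and *p* the response rate among the *N* − *a* who have it.

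Planned rate = *p*(*N* − *a*)/*N* = *p* × (1 − *a*/*N*)

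The plan states no expected value for this endpoint, so there is no figure of its own to reproduce. The documents give neither *a* nor *p*. The values below are assumptions chosen to show a range. Intervals are exact Clopper-Pearson 95% intervals, standing in for the Duffy and Santner intervals that the plan names.

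| Assumed *p* | Assumed *a* | Planned rate | Rate among patients with the component |
|---|---|---|---|
| 75% | 0 | 12/16 = 75.0% (47.6–92.7) | 12/16 = 75.0% (47.6–92.7) |
| 75% | 4 | 9/16 = 56.3% (29.9–80.2) | 9/12 = 75.0% (42.8–94.5) |
| 75% | 8 | 6/16 = 37.5% (15.2–64.6) | 6/8 = 75.0% (34.9–96.8) |
| 50% | 4 | 6/16 = 37.5% (15.2–64.6) | 6/12 = 50.0% (21.1–78.9) |
| 50% | 8 | 4/16 = 25.0% (7.3–52.4) | 4/8 = 50.0% (15.7–84.3) |
| 100% | 4 | 12/16 = 75.0% (47.6–92.7) | 12/12 = 100% (73.5–100) |

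Check of the formula in the second row: 0.75 × (1 − 4/16) = 0.75 × 0.75 = 0.5625.

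The bias is always downward, grows in proportion to the share without the component, and vanishes when *a* = 0.

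**4. The enhancing rate.** The same formula would apply if tumors with no enhancing part can enroll. Sections 3.3.2 and 11.2.1 do not require one. Section 11.4.1, however, describes measurable lesions as enhancing, and 3.3.2 refers the reader to Section 11.0. On that text an enhancing part is expected, though with no minimum enhancing volume. The documents leave this unsettled.

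**5. The primary endpoint.** Sections 13.2.1 and 11.4.5.4 use the volume of all measurable lesions. Every eligible patient has a measurable lesion, so the primary rate and its decision rules are not touched.

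**The case against.** The strongest counter-argument is that eligibility merely fails to exclude component-free tumors; nothing says any will be enrolled. Section 1.1 does remark that "Either the cystic, solid or both components, of craniopharyngiomas can cause significant symptomatic mass effect", but that describes which part causes symptoms, in craniopharyngiomas generally. It is not evidence that papillary tumors lack one part. This stands: the size of the effect is unknown and may be zero.

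A second argument is that a rate over all evaluable patients is a legitimate descriptive quantity, and that both rates are estimates with no test or decision attached. That limits the importance of the point but does not remove it. Objective 2.2.4 asks about activity on the component, and estimation is all that this endpoint offers. The detailed analysis plan promised in 13.4.2 is for the exploratory endpoints only.

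Three stronger readings are tempting, and the documents do not support them:

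- **Inflation through CR.** A reader might infer that an absent component could be scored as a complete response. Section 13.4.1 counts only decreasing volume, and CR in 11.4.5.4 is a disappearance, which presupposes something present at baseline.
- **Trace components.** A reader might infer that a tiny component could yield a PR on a trivial change. The Section 11.0 thresholds apply to measurable lesions, and the plan does not say that a smaller trace would be scored.
- **A confounded comparison.** A reader might infer that enhancing and non-enhancing response are to be set against each other. Objectives 2.2.3 and 2.2.4 stand separately, and no such comparison is planned.

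**Conclusion.** The point holds for the non-enhancing rate. As written, Section 13.4.1 understates response by the factor (1 − share without the component) whenever such patients are enrolled. Under the assumed inputs of 75% response and 4 of 16 without the component, that is 56% instead of 75%. Both inputs are assumptions; the documents supply only the 16.

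For the enhancing rate the point is conditional on how the conflict between 11.4.1 and Sections 3.3.2 and 11.2.1 is resolved. The consequence is confined to two descriptive secondary endpoints.

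**What to change.** In Section 13.4.1:

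- Use as denominator for each component rate the evaluable patients whose baseline central read shows that component at or above a prespecified minimum volume. A volume minimum suits a volumetric read better than the 10 mm two-dimensional rule, which was written for the whole lesion.
- State that patients below the minimum, including those with zero baseline volume, are outside that rate, and report their number per cohort.
- Keep the all-evaluable rate as a sensitivity analysis.

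Reconcile 11.4.1 with 3.3.2 and 11.2.1 on whether an enhancing part is required.

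The change is to analysis wording only. Appendix II already requires volumetric imaging to measure enhancing tumor and cysts, so no new data are needed. The cost is smaller denominators and generally wider intervals: in the illustration with 8 of 16 excluded, the interval width goes from 49.4 points (15.2 to 64.6) to 61.9 points (34.9 to 96.8).

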- \*\*\* Patients who progress or who do not progress within 2 years from registration, will be followed for survival every 6 months, for a maximum of 5 years from registration (step 1). Patients discontinuing for reasons other than progressive disease will be followed for progression every 16 weeks (+/- 4 weeks) until they have reached 2 years post-registration or until documented progression (whichever comes first), then followed for survival every 6 months, for a maximum of 5 years from registration (Step 1). See also [Section 12.0](#).
- 1 History & physical should include neurologic exam and assessment of endocrine therapy (including dosage and type the patient is receiving).
- 2 To be completed after pre-registration and  $\leq 21$  days prior to treatment, see [Appendix I](#).
- 3 Solicited AEs are to be collected starting at baseline. Routine AEs are to be collected starting after registration. See [Sections 9.1](#) and [9.2](#). See also AEs of special interest in [Section 9.3](#). See [Section 9.4](#) for expedited reporting of SAEs.
- 4 Albumin, alkaline phosphatase, total bilirubin, bicarbonate, BUN, calcium, chloride, creatinine, glucose, potassium, total protein, SGOT[AST], SGPT[ALT], sodium and CPK. Glucose must be fasting (i.e., 8 hours or more fast).
- 5 For women of childbearing potential. Must be done  $\leq 7$  days prior to registration and  $\leq 7$  days prior to initiation of vemurafenib and cobimetinib
- 6 See [Sections 4.3](#), [4.4](#) and [6.2](#) for central review submission.
- 7 Scans can include either: 1) MRI Brain or 2) CT Brain. CT should ONLY be used for patients unable to undergo MR imaging because of non-compatible device or life-threatening gadolinium allergy. Also see [Section 11.0](#). Supporting documentation is to be submitted, per [Section 6.1.1](#). **All MRIs must be performed per [Appendix II](#) and submitted to IROC Ohio. Response assessment should include assessment of all sites of disease.** Baseline scan should be submitted to IROC within 14 days after patient registration per [Section 6.3](#). Any images required per footnote E or that are part of clinical care should be submitted to IROC Ohio within 14 days after acquisition per [Section 6.3](#).
- 8 Oxygen saturation should be assessed at rest and after 1 minute walk. Dose modifications for hypoxia should be followed per [Section 8.2.2.15](#).

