- E Every 2 cycles (+/- 7 days) from baseline scan while receiving cobimetinib and vemurafenib. Patients who are noted to have PR or CR should have a confirmation scan performed 4-8 weeks (+/- 7 days) after the scan demonstrating response. Once patients on Cohort A complete treatment, staging scans must be performed every 16 weeks (+/- 4 weeks) (from last scan performed during treatment) until they have reached 2 years post-registration or until documented progression. Patients on Cohort B who receive surgery or radiation at investigator discretion must submit initial post-operative/post-RT scan, 1 year (+/- 14 days) post-op/post-RT scan and any other scans done as part of clinical care after surgery and radiation. Of note, surgery can be delayed by not more than 4 weeks to obtain a confirmatory scan to document a response. Patients discontinuing for reasons other than progressive disease will have staging scans every 16 weeks (+/- 4 weeks) until they have reached 2 years post-registration or until documented progression, whichever comes first.

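### Duration of response counts deaths up to 5 years but censors survivors at their last scan, due by 2 years off drug, so one late death can collapse the curve

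*Combined protocol and SAP*

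**What the plan says.** **Event and censoring.** In Section 13.4.1, duration of response runs from first CR or PR "until the first date that progressive disease or death is documented". Patients who fail to return for evaluation, and those who are alive and "have not progressed at the time of analysis will be censored for progression at the time of the last tumor assessment". The estimator is stated: "Duration of response will be estimated using the Kaplan-Meier method within each cohort". Medians and rates with 95% confidence intervals are planned.

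**Scans.** Section 5.0, footnote E, sets the on-drug schedule as "Every 2 cycles (+/- 7 days) from baseline scan while receiving cobimetinib and vemurafenib", with no end date. Patients who stop for reasons other than progression "will have staging scans every 16 weeks (+/- 4 weeks) until they have reached 2 years post-registration or until documented progression". Cohort A patients who complete treatment have the same 16-week schedule and the same 2-year end.

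**Survival.** The triple-asterisk footnote in Section 5.0 has patients "then followed for survival every 6 months, for a maximum of 5 years from registration (Step 1". The Schema also gives 5 years or death.

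**PFS.** Section 13.4.1 names Kaplan-Meier for PFS but states neither an event definition nor a censoring rule.

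**The concern.** Take two off-drug responders, both progression-free at their last scheduled scan near month 24. One dies at month 48 and the other is alive at year 5. Under the rule as written, the first stays at risk until month 48 and then counts as an event. The second leaves the risk set at about month 24. Which of them is in the late risk set is decided by what happens later, so censoring depends on the outcome, and Kaplan-Meier does not allow that. The death is also dated as though response had held throughout, although no scheduled scan could have shown otherwise.

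The tail of the curve and the median are at stake. In a single-arm trial of a tumor whose control may last beyond 2 years, readers will look at both to judge durability.

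**Working it through.** **1. The plan's own figures.** The documents give no figure for duration of response. The figures that can be checked are those of the two-stage design in Section 13.2: 9 then 16 patients, stop on 0 responses, succeed on at least 3. Exact binomial calculation gives alpha 0.0406 (stated 0.041), power 0.8864 at 30% (stated 0.886), early stopping 0.630 at 5% and 0.040 at 30%, and family-wise error 0.0795 (stated 0.08). All reproduce, and none depends on the rule at issue.

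**2. Inputs.**
- From the documents: the event and censoring rules, the 2-year scan horizon off drug, survival follow-up to 5 years, and at most 16 evaluable patients per cohort. The design alternative of 30% gives 0.30 × 16 = 4.8, about 5 responders.
- Assumed: response at month 2; survivors last scanned at month 24, so censored at 24 − 2 = 22 months of response; one death at month 48, or 48 − 2 = 46 months of response.

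**3. Kaplan-Meier under the stated rule.** S(t) is the product of (1 − d/n) over event times.
- 16 responders, no progression, one late death: at 46 months n = 1, so S = 1 × (1 − 1/1) = 0 and the median is 46 months. Cut at the scan horizon, S stays at 1.00 and the median is not reached. For contrast, following survivors to an assumed 58 months gives 1 − 1/16 = 0.9375.
- Two progressions added, at 8 and 14 months: 15/16 = 0.9375, then × 14/15 = 0.875, then 0 at 46 months. Cut at the horizon, S stays at 0.875 and the median is not reached.
- With 3, 8 or 14 responders, or a death at month 30 or 58, the risk set at the death is again 1 and S again falls to 0.

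**4. Patients still being scanned.** If k survivors are scanned beyond the time of the death, a curve otherwise at 1 falls to 1 − 1/(k + 1): 0.50 for k = 1, 0.67 for 2, 0.75 for 3 and 0.83 for 5. The false median remains at k = 1 and disappears from k = 2.

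**5. How often a late death occurs.** With n responders progression-free at 2 years and annual hazard h, the chance of at least one death in years 2 to 5 is 1 − exp(−3hn). For h = 1%, 2% and 5% this is 38%, 62% and 91% with n = 16, and 21%, 38% and 70% with n = 8.

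**6. How often the curve reaches 0.** The simulation assumed exponential progression with 60% or 80% progression-free at 24 months, all patients off drug, and no scans after month 24. Ranges run from a hazard of 1% to 5% per year.

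| Responders | Follow-up | Chance that S falls to 0 |
|---|---|---|
| 16 | 5 years for all | 24% to 81% |
| 5 | 5 years for all | about 10% to 43% |
| 16 | 3-year accrual, analysis at month 46 | about 5% to 28% |

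The true 5-year value in these scenarios is 22% to 54%: 0.6^2.5 × exp(−0.25) = 0.22 and 0.8^2.5 × exp(−0.05) = 0.54. Month 46 is 36 months of accrual, about 4 of treatment and the 6 named in Section 13.3.3.

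**The case against.** **The clause on patients who fail to return might already censor late deaths at the last scan.** This reading is possible but weak. A patient with no scan due has not failed to return, and the event clause names death without limit. Section 11.4.5.4 adds to the ambiguity by counting failure to return because of death as progression unless clearly unrelated to the tumor.

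**Imaging does not simply stop at 2 years.** This stands in part. On-drug scans continue, and Section 12.1.1 lets Cohort B stay on drug until progression. Footnote 7 of Section 5.0 asks for images from clinical care with no 2-year limit, and clear clinical worsening is progression without a scan. A reader might infer that nobody looks after 2 years; the documents support only that scheduled off-drug scans end then. Cohort A normally stops after 4 or 5 cycles, so nearly all of it remains exposed.

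**The largest percentages may not apply.** This stands. A reader might take 24% to 81% as the expected error. Those figures need 16 responders and 5 years of follow-up for everyone. No section sets the analysis at 60 months, and no section gives a death hazard.

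**PFS.** A reader might infer that PFS has the same defect. The documents do not show this, because they give PFS no censoring rule to examine. They show a gap.

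**Importance.** Duration of response is a descriptive secondary endpoint with no formal comparison between cohorts, and a risk set of one is visible if numbers at risk are shown. Section 13.2.3 decides on response counts alone. All of this stands.

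**Conclusion.** The concern holds for duration of response. Following Section 13.4.1 as written, together with the Section 5.0 calendar, makes censoring depend on the outcome after the off-drug scan horizon. A single late death can then take the curve to 0, or to 0.50 with one other patient at risk, and produce a median that the data do not support. The mechanism follows from the documents. Its frequency does not: it depends on the number of responders, the death hazard and the analysis date, none of which they fix. The table gives the range under stated assumptions, and clinical-care or on-drug scans would lower it. The damage is confined to the tail and median of a secondary endpoint. It should be corrected before analysis, but it does not threaten the trial's main conclusion.

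**What to change.** In Section 13.4.1:

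1. For off-drug patients, censor duration of response administratively at the end of scheduled imaging, 2 years after registration, converted for each patient to time from response. The curve starts at response, so a fixed 24 months from registration is not a point on it.
2. Count progression or death up to that date as events. Censor patients who die later at their last tumor assessment on or before it, and keep those deaths for overall survival only.
3. Report no median or rate beyond the horizon except where patients still scanned on drug support it, and show numbers at risk.
4. Give PFS the same event and censoring rule, with time measured from registration.

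A rule that only counts deaths within two scan intervals of the last scan, 2 × (16 + 4) = 40 weeks, is not enough. Survivors would still leave at about month 24, and with 16 patients and 5-year follow-up the curve would still reach 0 in about 8% to 36% of simulated trials.

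A small asymmetry remains between each patient's last scan and the 2-year date. If scans are done on schedule, it spans at most about 16 + 4 = 20 weeks, and the numbers at risk will show it.

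The cost is wording, with no extra scans or visits. The downside is that duration of response and PFS are reported only to about 2 years for off-drug patients, which is as far as the scheduled imaging reaches.
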